12. REFERENCES

13. TABLES, FIGURES AND LISTINGS

13.1. Specific Presentation Details

Tables, Listings and Figures will be provided in pdf and WORD format. All summary Tables and Figures will have source data footnotes that refer to the relevant Listings. Dates will appear as DDMMYYYY and times as hh:mm (24-hour clock times). All Listings will be ordered by cohort, subject number and scheduled visit. Any unscheduled visit information will also be included within the Listings, identified as unscheduled.

For the presentation of summary data, values will be aligned based on the unit column, and not left/right justified. For example:

Parameter	n	xx	xx
	Mean (SD)	xx.x (xx.xx)	xx.x (xx.xx)
	Median	xx.x	xx.x
[optional]	GM (GSD)	xx.x	xx.x
	Q1, Q3	xx.x, xx.x	xx.x, xx.x
	Min, Max	xx, xx	xx, xx

All Tables, Listings and Figures will have the SAS program name, output filename and date of production in the footnote.

All Tables, Listings and Figures will include the following study header and footer:

CONFIDENTIAL

Mereo Biopharma
MPH313-1-02

Page x of y

Table x.x
Title
Population

Source Data: Listing 16.2.x {Source data footnote only appears for tables, where x references relevant listing number}

Program: XXXXXXXXX

Output: XXXXXX

Date: XXXXXXXXX

13.2. List of Tables

Table Number	Table Title
14.1.1	Participant Disposition – All Subjects
14.1.2.1	Demography – Safety Analysis Set
14.1.2.2	Demography of Cohort F – Safety Analysis Set
14.1.3.1	Baseline Disease Characteristics – Safety Analysis Set
14.1.3.2	Baseline Disease Characteristics of Cohort F – Safety Analysis Set
14.1.4.1	Prior Cancer Treatments – Safety Analysis Set
14.1.4.2	Other Prior Medications – Safety Analysis Set
14.1.4.3	Concomitant Medications – Safety Analysis Set
14.1.5	Investigational Product Exposure – Safety Analysis Set
14.2.1	Response – (RECIST v1.1) – Response Evaluable Analysis Set
14.2.2.1	Duration of Response (RECIST v1.1) – Response Evaluable Analysis Set
14.2.2.2	Duration of Response (RECIST v1.1) – KM – Response Evaluable Analysis Set
14.2.3.1	Duration of Stable Disease (RECIST v1.1) – Response Evaluable Analysis Set
14.2.3.2	Duration of Stable Disease (RECIST v1.1) – KM – Response Evaluable Analysis Set
14.2.4	Response – (iRECIST) – Response Evaluable Analysis Set
14.2.5.1	Duration of Response (iRECIST) – Response Evaluable Analysis Set
14.2.5.2	Duration of Response (iRECIST) – KM – Response Evaluable Analysis Set
14.2.6.1	Duration of Stable Disease (iRECIST) – Response Evaluable Analysis Set
14.2.6.2	Duration of Stable Disease (iRECIST) – KM – Response Evaluable Analysis Set
14.2.7	Progression Free Survival (RECIST) – KM – Response Evaluable Analysis Set
14.2.8	Progression Free Survival (iRECIST) – KM – Response Evaluable Analysis Set
14.2.9	Overall Survival – KM – Response Evaluable Analysis Set
14.3.1.1	Overall Summary of Treatment Emergent Adverse Events – Safety Analysis Set

Table Number	Table Title
14.3.1.2	Treatment Emergent Adverse Events by System Organ Class and Preferred Term – Safety Analysis Set
14.3.1.3	Treatment Emergent Adverse Events by System Organ Class, Preferred Term and Severity – Safety Analysis Set
14.3.1.4.1	Treatment Emergent Adverse Events Related to Etigilimab by System Organ Class and Preferred Term – Safety Analysis Set
14.3.1.4.2	Treatment Emergent Adverse Events Related to Nivolumab by System Organ Class and Preferred Term – Safety Analysis Set
14.3.1.4.3	Treatment Emergent Adverse Events Related to Etigilimab and Nivolumab by System Organ Class and Preferred Term – Safety Analysis Set
14.3.1.4.4	Treatment Emergent Adverse Events Related to Etigilimab or Nivolumab by System Organ Class and Preferred Term – Safety Analysis Set
14.3.1.5	Serious Treatment Emergent Adverse Events by System Organ Class and Preferred Term – Safety Analysis Set
14.3.1.6.1	Serious Treatment Emergent Adverse Events Related to Etigilimab by System Organ Class and Preferred Term – Safety Analysis Set
14.3.1.6.2	Serious Treatment Emergent Adverse Events Related to Nivolumab by System Organ Class and Preferred Term – Safety Analysis Set
14.3.1.6.3	Serious Treatment Emergent Adverse Events Related to Etigilimab and Nivolumab by System Organ Class and Preferred Term – Safety Analysis Set
14.3.1.6.4	Serious Treatment Emergent Adverse Events Related to Etigilimab or Nivolumab by System Organ Class and Preferred Term – Safety Analysis Set
14.3.1.7.1	Treatment Emergent Adverse Events that Led to Treatment Discontinuation by System Organ Class and Preferred Term – Safety Analysis Set
14.3.1.7.2	Treatment Emergent Adverse Events that Led to Withdrawal from the Study by System Organ Class and Preferred Term – Safety Analysis Set
14.3.1.7.3	Treatment Emergent Adverse Events that Led to Death by System Organ Class and Preferred Term – Safety Analysis Set
14.3.1.8.1	Treatment Emergent Adverse Events of Special Interest (Infusion or Immune Related) by System Organ Class and Preferred Term – Safety Analysis Set
14.3.1.8.2	Treatment Emergent Adverse Events of Special Interest (Infusion Related) by System Organ Class and Preferred Term – Safety Analysis Set
14.3.1.8.3	Treatment Emergent Adverse Events of Special Interest (Immune Related) by System Organ Class and Preferred Term – Safety Analysis Set

Table Number	Table Title
14.3.1.9	Overall Summary of Treatment Emergent Adverse Events Regardless of Subsequent Cancer Treatment – Safety Analysis Set
14.3.1.10	Treatment Emergent Adverse Events Regardless of Subsequent Cancer Treatment by System Organ Class and Preferred Term – Safety Analysis Set
14.3.2.1	Haematology Parameters Summary – Safety Analysis Set
14.3.2.2	Biochemistry Parameters Summary – Safety Analysis Set
14.3.2.3	Coagulation Parameters Summary – Safety Analysis Set
14.3.2.4	Thyroid Function Parameters Summary – Safety Analysis Set
14.3.3	Vital Signs Parameters Summary – Safety Analysis Set
14.3.4	ECOG Performance Status – Shift from Baseline – Safety Analysis Set
14.3.5	Electrocardiogram Parameters Summary – Safety Analysis Set

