9. STUDY ANALYSIS SETS

The populations defined below will be reviewed against the study database at a DRM at the time of the Final Analysis. The database at this time will be nearly final (i.e., the meeting may result in further data queries/changes post meeting), so inclusion/exclusion of subjects from study populations defined at this meeting will be further checked (post meeting) against a final locked database and will then be finalised prior to reporting.

The following analysis sets are defined:

Population	Description
Safety Analysis Set	All subjects who received any amount of study drug. All safety analyses will be performed using the Safety analysis set.
Intention to Treat (ITT) Analysis Set	All subjects who signed an informed consent form and were enrolled into the study.
Response-Evaluable (RE) Analysis Set	The Response-Evaluable analysis set is a modified ITT analysis set defined as all subjects with measurable disease at baseline who received study drug and had at least one post-baseline response assessment or discontinued treatment due to disease progression (including death due to disease progression) within 16 weeks (+ a 2-week window) of the first dose of study drug. All efficacy analyses will be performed using the Response-Evaluable analysis set

10.PLANNED STATISTICAL METHODS

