If a subject does not have a disease assessment after their first treatment they will be censored at the date of their first treatment.

If a subject initiates another cancer treatment prior to iCPD/death they will be censored at the last assessment prior to initiation of the alternative cancer treatment.

If a subject experiences iCPD or death immediately following 2 or more visits at which their response was missing or NE they will be censored at the time of their last assessment prior to missing/NE response.

10.8.3.5. *Overall Survival*

Overall survival (OS) is defined as the time from the first dose of study drug to death due to any cause.

For analysis of OS, all subjects will be followed for survival for up to 2 years, until withdrawal of consent, loss to follow up, or death, whichever occurs first. At the time of analysis of OS, any subjects who remain alive will be censored at the last date they were known to be alive.

The duration will be calculated (in days) as:

Date of death due to any cause – Date of first treatment.

Overall Survival will be summarised by cohort, and sub-cohort for cohort F, using descriptive summaries, which will not account for censoring. Additionally, Kaplan-Meier curves will be produced for each cohort, and sub-cohort for cohort F, along with a table summarising the median and 25th and 75th percentiles of the overall survival, inclusive of censoring, for each cohort, including sub-cohort.

[Kaplan-Meier plot: y-axis = cumulative proportion of participants who are alive, x-axis = day, one line for each cohort, including sub-cohort, overlayed on the same plot].

Censoring

If a subject is still alive at the end of follow-up they will be censored at the date they were last known to be alive.

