13.3. List of Figures

Figure Number	Figure Title
14.1.1	Swimmer Plot of Study Progression – Response-Evaluable Analysis Set
14.1.2	Swimmer Plot of Study Progression – Gynaecological Indications – Response-Evaluable Analysis Set
14.1.3	Swimmer Plot of Study Progression – Rare Tumors – Response-Evaluable Analysis Set
14.2.1.1	Waterfall Plot of Percentage Change from Baseline in the Sum of Diameters – Response-Evaluable Analysis Set
14.2.1.2	Waterfall Plot of Percentage Change from Baseline in the Sum of Diameters – Gynaecological Indications – Response-Evaluable Analysis Set
14.2.1.3	Waterfall Plot of Percentage Change from Baseline in the Sum of Diameters – Rare Tumors – Response-Evaluable Analysis Set
14.2.2.1	Spider Plot of Percentage Change from Baseline in the Sum of Diameters Over Time – Response-Evaluable Analysis Set
14.2.2.1	Spider Plot of Percentage Change from Baseline in the Sum of Diameters Over Time – Gynaecological Indications – Response-Evaluable Analysis Set
14.2.2.1	Spider Plot of Percentage Change from Baseline in the Sum of Diameters Over Time – Rare Tumors – Response-Evaluable Analysis Set
14.2.3.1	Kaplan-Meier Plot of Duration of Response – Response-Evaluable Analysis Set
14.2.3.2	Kaplan-Meier Plot of Duration of Stable Disease – Response-Evaluable Analysis Set
14.2.3.3	Kaplan-Meier Plot of Duration of Response (iRECIST) – Response-Evaluable Analysis Set
14.2.3.4	Kaplan-Meier Plot of Progression Free Survival – Response-Evaluable Analysis Set
14.2.3.5	Kaplan-Meier Plot of Progression Free Survival (iRECIST) – Response-Evaluable Analysis Set
14.2.3.6	Kaplan-Meier Plot of Overall Survival – Response-Evaluable Analysis Set

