14. TABLE AND LISTING SHELLS

Table 14.1.1
Participant Disposition
All Participants

	Cohort A EC CPI-Nai (N = XX) n (%)	Head and Neck (N = XX) n (%)	Cohort C Cervical (N = XX) n (%)	Cohort E TMB-H/MSS (N = XX) n (%)	Cohort F Rare Tumors (N = XX) n (%)	Cohort G Post-CPI (N = XX) n (%)	Cohort H Ovarian (N = XX) n (%)	Total (N = XX) n (%)
Screened	X	X	X	X	X	X	X	X
Screen Failure	X	X	X	X	X	X	X	X
Intention-to-Treat Analysis Set [1]	X	X	X	X	X	X	X	X
Safety Analysis Set [2]	X (XX.X)	X (XX.X)	X (XX.X)	X (XX.X)	X (XX.X)	X (XX.X)	X (XX.X)	X (XX.X)
Response-Evaluable Analysis Set [3]	X (XX.X)	X (XX.X)	X (XX.X)	X (XX.X)	X (XX.X)	X (XX.X)	X (XX.X)	X (XX.X)
Received at Least One Dose of								
Etigilimab	X (XX.X)	X (XX.X)	X (XX.X)	X (XX.X)	X (XX.X)	X (XX.X)	X (XX.X)	X (XX.X)
Nivolumab	X (XX.X)	X (XX.X)	X (XX.X)	X (XX.X)	X (XX.X)	X (XX.X)	X (XX.X)	X (XX.X)
Completed all Dosing Cycles	X (XX.X)	X (XX.X)	X (XX.X)	X (XX.X)	X (XX.X)	X (XX.X)	X (XX.X)	X (XX.X)
Completed Treatment Termination Visit	X (XX.X)	X (XX.X)	X (XX.X)	X (XX.X)	X (XX.X)	X (XX.X)	X (XX.X)	X (XX.X)
Completed Follow-up Visit	X (XX.X)	X (XX.X)	X (XX.X)	X (XX.X)	X (XX.X)	X (XX.X)	X (XX.X)	X (XX.X)
Discontinued Treatment	X (XX.X)	X (XX.X)	X (XX.X)	X (XX.X)	X (XX.X)	X (XX.X)	X (XX.X)	X (XX.X)
Reason for Discontinuation								
XXXXX	X (XX.X)	X (XX.X)	X (XX.X)	X (XX.X)	X (XX.X)	X (XX.X)	X (XX.X)	X (XX.X)
XXXXX	X (XX.X)	X (XX.X)	X (XX.X)	X (XX.X)	X (XX.X)	X (XX.X)	X (XX.X)	X (XX.X)
XXXXX	X (XX.X)	X (XX.X)	X (XX.X)	X (XX.X)	X (XX.X)	X (XX.X)	X (XX.X)	X (XX.X)
XXXXX	X (XX.X)	X (XX.X)	X (XX.X)	X (XX.X)	X (XX.X)	X (XX.X)	X (XX.X)	X (XX.X)
Discontinued Study	X (XX.X)	X (XX.X)	X (XX.X)	X (XX.X)	X (XX.X)	X (XX.X)	X (XX.X)	X (XX.X)
Reason for Discontinuation								
XXXXX	X (XX.X)	X (XX.X)	X (XX.X)	X (XX.X)	X (XX.X)	X (XX.X)	X (XX.X)	X (XX.X)
XXXXX	X (XX.X)	X (XX.X)	X (XX.X)	X (XX.X)	X (XX.X)	X (XX.X)	X (XX.X)	X (XX.X)
XXXXX	X (XX.X)	X (XX.X)	X (XX.X)	X (XX.X)	X (XX.X)	X (XX.X)	X (XX.X)	X (XX.X)
XXXXX	X (XX.X)	X (XX.X)	X (XX.X)	X (XX.X)	X (XX.X)	X (XX.X)	X (XX.X)	X (XX.X)

[1] Intention-to-Treat Analysis Set: All subjects who signed an informed consent form and were enrolled into the study.

[2] Safety Analysis Set: All subjects who received any amount of study drug.

[3] Response Evaluable Analysis Set: All subjects with measurable disease at baseline, with at least one post-baseline response assessment or discontinues treatment due to disease progression or death within 16 weeks of first dose of study drug.

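### Overall survival is timed from first dose but analysed only in the Response-Evaluable set, which is defined by events after dosing, so some treated subjects, including all of Cohort B, have no survival result

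*SAP*

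**What the plan says.** SAP 10.8.3.5 gives the endpoint: "Overall survival (OS) is defined as the time from the first dose of study drug to death due to any cause". It adds: "For analysis of OS, all subjects will be followed for survival for up to 2 years". Protocol 9.3.1 has the same definition, and Protocol 4.2 sends everyone who stops treatment into survival follow-up.

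The outputs are narrower. SAP 13.2 lists one OS table, 14.2.9, titled "Overall Survival – KM – Response Evaluable Analysis Set". SAP 13.3 lists one OS figure, 14.2.3.6, titled "Kaplan-Meier Plot of Overall Survival – Response-Evaluable Analysis Set". No OS output is listed for the ITT or Safety set.

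SAP Section 9 requires, for the Response-Evaluable set, measurable disease at baseline, receipt of study drug, and that the subject "had at least one post-baseline response assessment or discontinued treatment due to disease progression (including death due to disease progression) within 16 weeks" of first dose, with a 2-week window. It then states: "All efficacy analyses will be performed using the Response-Evaluable analysis set". Protocol 9.2 has the same rule, so the SAP follows the protocol here. SAP Section 11 records no change of population.

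The footnotes to Table 14.1.1 and Listing 16.2.3 word the second route differently: "discontinues treatment due to disease progression or death within 16 weeks of first dose of study drug".

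**The concern.** OS needs no scan. The clock starts at first dose, but entry to the analysis depends on what happens afterwards. A subject who qualifies through a scan must have lived until it. A treated subject with no scan, whose stopping or death is not attributed to progression, is removed even when the date of death is known. That is selection on post-baseline events, often called guarantee-time or immortal-time bias.

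At stake is what the OS curve describes. As planned, it shows survival among subjects who were assessed or who stopped or died through progression. The SAP defines it as survival from first dose among subjects who were treated and followed. Cohorts are small (10 subjects in stage 1), so one or two exclusions can move a curve visibly.

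**Working it through.** **The plan's own figures.** The only design figures stated are for the Simon two-stage response designs. An exact two-stage binomial calculation (the sum over stage-1 counts that continue of the stage-1 probability times the stage-2 tail) gives alpha 0.04683 and power 0.8011 for Type 1, and 0.04709 and 0.8051 for Type 2. These match the stated 0.0468 and 80.11%, and 0.0471 and 80.51%. They concern response only. The documents give no OS assumption, event count or precision target.

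**Who is kept and who is dropped** (treated, measurable disease, no post-baseline assessment), under SAP Section 9:

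- Stops for, or dies of, progression within 16 (+2) weeks: kept.
- Dies of another cause: dropped.
- Stops for toxicity, withdrawal or loss to follow-up: dropped, whatever the later survival.

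Under the footnote wording, the second group may be kept if death comes within 16 weeks. The third group stays out unless that wording is stretched to deaths after treatment has stopped.

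**Evidence that the exclusion occurs.** SAP 10.1.2 drops a cohort from displays when it has no subjects and applies this to Cohort D. Cohort B keeps its column in the Safety-set shells. The Response-Evaluable shells, including the shell for Table 14.2.2.2 that is reused for Table 14.2.9, note that no Cohort B subject is in the set. Cohort B therefore has safety results but no OS result. The number of its subjects is not given.

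**Size if the dropped subjects are early deaths (illustration).** Assume exponential survival with median M, and let a fraction q of treated subjects die before the first scan and be dropped. After that scan:

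- S_RE(t) = S(t)/(1 − q)
- median_RE = M × log2(2/(1 − q)), a rise of log2(1/(1 − q)) whatever M is

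Inputs are q = 10/125 = 0.08 (125 enrolled and 115 evaluable, Protocol 2.1) and M = 205 days (earlier study, combination part, Protocol 1.2; used only as an assumed level).

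- log2(1/0.92) = 0.120, a rise of 12.0%
- 205 × 1.120 = 230 days

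In a 10-subject cohort, one dropped early death multiplies later survival estimates by 1/(1 − 0.1) = 10/9.

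Alternatively, work from deaths before the Week 8 scan (Day 57): 1 − 2^(−57/205) = 17.5% of subjects. If only a share of these is dropped:

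| Share of pre-scan deaths dropped | Subjects dropped | Median, days |
|---|---|---|
| 10% | 1.8% | 210 |
| 20% | 3.5% | 216 |
| 30% | 5.3% | 221 |
| 50% | 8.8% | 232 |

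**Direction if the dropped subjects leave alive.** Let 8% leave alive with hazard h times that of the rest, and let the Response-Evaluable median be 205 days. The all-treated median t solves 0.92 × 2^(−t/205) + 0.08 × 2^(−ht/205) = 0.5. For h = 0.5, 1 and 2, t = 215, 205 and 193 days. The present analysis then understates, matches or overstates survival.

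**The case against.** Several objections have force.

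- **The definition is less severe than it first looks.** A reader might infer that every treated subject who dies or leaves before the first scan disappears from OS. The documents do not support that. Early deaths and discontinuations from progression are kept. Protocol 8.1 and 8.2 also schedule a tumor assessment at treatment termination (unless one was done in the preceding 14 days or progression was already documented), and SAP 10.1.1 uses unscheduled data for efficacy. Many early leavers should therefore become evaluable. This stands, and it reduces the number affected. It does not bring in those who die or leave without that scan.
- **Direction.** A reader might also infer that survival is overstated in every cohort. The leave-alive calculation shows that this depends on who is dropped. This stands.
- **Size.** The 10 of 125 is enrolled minus evaluable completers. It may include never-dosed subjects, who would be outside the Safety set too, and nothing says that these 10 die early. The earlier study's OS text is a weak guide: its Phase 1a OS rates repeat its PFS rates, and 30.0% alive at 3 months cannot fit a 173-day median. For Phase 1b it reports 57.9% at 3 months, where the exponential curve with a 205-day median gives 73.5% at Day 91. This stands.
- **Safety is not hidden.** Adverse events leading to death are tabulated in the Safety set (Table 14.3.1.7.3), deaths are listed (Listing 16.2.1.2), and Table 14.1.1 gives the size of each set by cohort. This stands.
- **Consequence.** OS is exploratory, with no hypothesis test and no decision rule. The population was prespecified in the protocol. This limits the priority of the change, but it does not make the population suitable for OS.

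**Conclusion.** The point holds in a limited form. OS is defined for treated subjects from first dose, but it is reported only for a set chosen partly by later events, and no all-treated version is planned. By the SAP's own shells, one treated cohort has no OS result at all.

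Overstatement is the likely direction, because removing an early death always lifts the later curve. It is not established for every cohort. The size cannot be determined from the documents. The 12% figure assumes exponential survival and that all 10 planned non-evaluable subjects are treated early deaths. The 210 to 232 day range assumes in addition a 205-day median and a dropped share of 10% to 50%.

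The primary response rate and its Simon boundaries are unaffected. The change is worth making because it is cheap and uses data already collected.

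**What to change.** 1. Change the population of Table 14.2.9 and Figure 14.2.3.6 to the Safety Analysis Set, and say so in SAP 10.8.3.5. Keep the Response-Evaluable versions as supplementary.
2. Do the same for PFS (Tables 14.2.7 and 14.2.8, Figures 14.2.3.4 and 14.2.3.5), which also starts at first treatment. Expect a smaller effect: SAP 10.8.3.3 and 10.8.3.4 censor subjects with no later assessment at first treatment and count only deaths within 30 days of the last tumor assessment.
3. Record both in SAP Section 11 as a change from the population rule in Protocol 9.2, and amend the matching sentence in SAP Section 9.
4. Reconcile the footnotes to Table 14.1.1 and Listing 16.2.3 with SAP Section 9, so that it is clear whether a death not due to progression qualifies and whether the 2-week window applies.
5. Restore the Cohort B column in the OS and PFS shells.

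The cost is SAP wording, output titles and some extra programming, with no new data or patients. OS may look slightly less favourable, and its N will differ from that in the response tables, which a footnote can explain.

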13.3. List of Figures

Figure Number	Figure Title
14.1.1	Swimmer Plot of Study Progression – Response-Evaluable Analysis Set
14.1.2	Swimmer Plot of Study Progression – Gynaecological Indications – Response-Evaluable Analysis Set
14.1.3	Swimmer Plot of Study Progression – Rare Tumors – Response-Evaluable Analysis Set
14.2.1.1	Waterfall Plot of Percentage Change from Baseline in the Sum of Diameters – Response-Evaluable Analysis Set
14.2.1.2	Waterfall Plot of Percentage Change from Baseline in the Sum of Diameters – Gynaecological Indications – Response-Evaluable Analysis Set
14.2.1.3	Waterfall Plot of Percentage Change from Baseline in the Sum of Diameters – Rare Tumors – Response-Evaluable Analysis Set
14.2.2.1	Spider Plot of Percentage Change from Baseline in the Sum of Diameters Over Time – Response-Evaluable Analysis Set
14.2.2.1	Spider Plot of Percentage Change from Baseline in the Sum of Diameters Over Time – Gynaecological Indications – Response-Evaluable Analysis Set
14.2.2.1	Spider Plot of Percentage Change from Baseline in the Sum of Diameters Over Time – Rare Tumors – Response-Evaluable Analysis Set
14.2.3.1	Kaplan-Meier Plot of Duration of Response – Response-Evaluable Analysis Set
14.2.3.2	Kaplan-Meier Plot of Duration of Stable Disease – Response-Evaluable Analysis Set
14.2.3.3	Kaplan-Meier Plot of Duration of Response (iRECIST) – Response-Evaluable Analysis Set
14.2.3.4	Kaplan-Meier Plot of Progression Free Survival – Response-Evaluable Analysis Set
14.2.3.5	Kaplan-Meier Plot of Progression Free Survival (iRECIST) – Response-Evaluable Analysis Set
14.2.3.6	Kaplan-Meier Plot of Overall Survival – Response-Evaluable Analysis Set

13.4. List of Listings

Listing Number	Listing Title
16.2.1.1	Subject Disposition
16.2.1.2	Survival and Follow-up Status
16.2.1.3	Failed Inclusion and Exclusion Criteria
16.2.2	Important Protocol Deviations
16.2.3	Subject Populations
16.2.4.1	Demographic Characteristics
16.2.4.2	Cancer Diagnosis
16.2.4.3	Cancer on Entry Into Study
16.2.4.4.1	Medical and Surgical History
16.2.4.4.2	Prior Biologic or Immune Therapy Cancer Treatments
16.2.4.4.3	Prior Systemic Chemotherapy Cancer Treatments
16.2.4.4.4	Prior Surgical Cancer Treatments
16.2.4.4.5	Prior Radiotherapy Cancer Treatments
16.2.4.4.6	Other Prior and Concomitant Medications
16.2.5.1	Study Drug Infusion – Etigilimab
16.2.5.2.2	Study Drug Infusion – Nivolumab
16.2.6.1.1	Screening Tumor Tissue Sample Collection
16.2.6.1.2	On-Treatment Tumor Tissue Sample Collection
16.2.6.1.3	Tumor Markers
16.2.6.1.4	Screening Contrast Enhanced Head CT or MRI Scan
16.2.6.2.1	Tumor Evaluation – Target Lesions

Listing Number	Listing Title
16.2.6.2.2	Tumor Evaluation – Non-Target Lesions
16.2.6.2.3	Tumor Evaluation – New Lesions
16.2.6.3.1	Tumor Response Evaluation (RECIST v1.1)
16.2.6.3.2	Tumor Response Evaluation (iRECIST)
16.2.6.4.1	Overall Response (RECIST v1.1)
16.2.6.4.2	Overall Response (iRECIST)
16.2.7	Adverse Events
16.2.8.1	Haematology
16.2.8.2	Biochemistry
16.2.8.3	Coagulation
16.2.8.4	Urinalysis
16.2.8.5	Thyroid Function
16.2.9.1	Other Laboratory Tests: Pregnancy
16.2.9.2	Other Blood Sample Collection
16.2.10	Vital Signs
16.2.11	ECOG Performance Status
16.2.12	Electrocardiogram
16.2.13	Transfusions
16.2.14	Subsequent Cancer Treatment
16.2.15	Visit Dates

